Comparative effectiveness of energy doses in critical illness

Short title: The Energy Dose Study

Principal Investigator: [name].

Protocol Version Date: 6/2/2014

NCT Number: NCT01369147

Abstract:

Protein and/or energy deficits are associated with increased rates of hospital infection, skeletal muscle weakness, impaired wound healing, and prolonged convalescence in ICU patients. To prevent or treat malnutrition, enteral nutrition (EN) and/or parenteral nutrition (PN) are routinely given worldwide to a significant proportion of ICU patients. Optimal caloric requirements in critically ill patients are unknown due to a lack of rigorous randomized clinical trials. The comparative efficacy of energy doses in critically ill patients is unknown and clinical recommendations are conflicting and controversial; this issue is the focus of our study.

We have designed this pilot, single-center Randomized Clinical Trial (RCT) to prospectively compare, for the first time, the clinical efficacy of different energy doses in ICU patients requiring PN due to intestinal failure/dysfunction. A total of 60 patients will be studied (20 per energy dose group) to generate critical preliminary data needed to inform subsequent appropriately powered Phase III multicenter trials.

The primary aim of this study is to perform a controlled, double-blind, prospective, randomized, intent-to-treat Phase II clinical trial to test the efficacy of three specific energy doses [0.6, 1.0 and 1.3 x measured REE (resting energy expenditure), respectively], given for 28 consecutive days during the ICU course, on 28-day total hospital-acquired infections (primary endpoint), Blood Stream Infections (BSI), and other important clinical outcomes in medical/surgical ICU patients requiring specialized parenteral \pm enteral feeding. We would also determine, in these subjects A) the impact of cumulative and mean daily 28-day energy deficits [energy intake-measured REE] on clinical outcome endpoints; and B) the practical utility of estimated REE determined by Harris-Benedict equation versus measured REE across different energy doses. We would also like to determine the impact of administered energy dose and energy deficits on global metabolomic patterns over time and their association with key clinical outcomes.

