Exclusion criteria: 1) The patient is pregnant; 2) The patient has unresuscitated clinical sepsis [defined as unstable blood pressure despite vasopressor support and mean arterial pressure (MAP) < 60 mm Hg on at least 3 consecutive readings within a 3-hour period during the 24 hours prior to study entry; 3); 3) The patient was admitted to the ICU following trauma or burns; 4) The patient has significant renal dysfunction (defined as serum creatinine > 2.5 mg/dL or deemed to have significant acute kidney injury by the primary physicians) and is not receiving continuous renal replacement therapy (CRRT) or intermittent hemodialysis; 5) The patient has previously undergone an organ transplantation; 6) the patient has a current malignancy or is currently receiving an active regimen of chemotherapy and/or radiotherapy to treat a previously diagnosed malignancy[#]; 7) the patient has a history of HIV/AIDS; 8) The patient has received any investigational drug within 60 days prior to study entry; and 9) The patient is unable or unwilling to participate in study procedures such as longitudinal blood draws and administration of study nutrient formulations.

[#] [†] Patients with malignant metastasis and terminal untreatable carcinoma will be excluded.

If the patient meets criteria, we will consent the patient's legally authorized representative (LAR), as potential study subjects will be mechanically ventilated and probably sedated.

Randomization of study subjects: A research team member will calculate the APACHE II score. Treatment assignments will be stratified according to clinical center and on the basis of illness severity (APACHE II score, either ≤ 15 or > 15). The treatment assignments will be generated by the Emory-based DCC with the use of a pseudo-random-number generator with randomly permuted blocks that will be used to ensure balance between the numbers of subjects assigned to the REE x 0.6, 1.0 or 1.3 groups, respectively.

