Twenty-eight day mortality will be summarized as a proportion plus the 95% confidence interval (overall and for each treatment group). The 28-day mortality will be compared between treatment groups using a chi-square or Fisher's exact test. The potential association of each of the categorical prognostic factors (gender, race, high or low Apache score, clinical center) with mortality will also be evaluated using a Chi-square test or Fisher's exact test. Baseline continuous prognostic factors (age, SOFA score, blood glucose) will be compared by treatment group using the Wilcoxon rank-sum test. Odds ratios will be calculated to measure the degree of association. All statistical tests will be 2-sided. Factors significant to at least a value of $P \leq 0.20$ in the univariable analyses will be used in multivariable logistic regression analyses. Forward and backward stepwise selection will be used if necessary to choose prognostic variables for a multivariable logistic regression model. The odds ratio and its 95% confidence interval will be calculated for each factor in the presence of others in the final model.

Days on mechanical ventilation, length of ICU stay and hospital length of stay will be summarized with percentiles (25th, 50th and 75th) and the median absolute deviation. These secondary outcomes will be compared between the 3 treatment groups using the Kruskal-Wallis test. Repeated-measures analyses of daily SOFA scores and laboratory measures such as blood glucose will be analyzed with a means model with SAS Proc Mixed (version 9, mixed linear models) providing separate estimates of the means by time on study (days 0, 3, 7, 14, 21, and 28) and treatment group (energy dose: 0.6, 1.0 and 1.3 x REE). An unstructured variance-covariance form among the repeated measurements will be assumed for each outcome and estimates of the standard errors of parameters will be used to perform statistical tests and construct 95% confidence intervals. T-tests will be used to compare the pairwise differences between the model-based treatment means (least-squares means) at each time point. Statistical tests will be 2-sided. The model-based means are unbiased with unbalanced and missing data, so long as the missing data are non-informative (missing at random). A dropout process is assumed to be missing at random if; conditional on the observed data, the dropout is independent of the unobserved measurements.

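### Age, SOFA score and blood glucose are screened for the mortality model by a comparison between randomised arms, which cannot show whether they predict death

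*Combined protocol and SAP*

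**What the plan says.** The paragraph on 28-day mortality in the Statistical Analysis section (Aim 1) sets out a sequence of steps.

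1. Mortality is compared between arms with a chi-square or Fisher's exact test.
2. The categorical prognostic factors are related to death: "gender, race, high or low Apache score, clinical center) with mortality will also be evaluated using a Chi-square test or Fisher's exact test".
3. For the continuous factors the grouping changes: "Baseline continuous prognostic factors (age, SOFA score, blood glucose) will be compared by treatment group using the Wilcoxon rank-sum test".
4. A general sentence follows: "Odds ratios will be calculated to measure the degree of association".
5. Factors that reach P ≤ 0.20 "in the univariable analyses will be used in multivariable logistic regression analyses", with forward and backward stepwise selection if needed.

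The next paragraph, on ventilation days and lengths of stay, names a different test where the arms are meant: "These secondary outcomes will be compared between the 3 treatment groups using the Kruskal-Wallis test".

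**The concern.** Step 5 needs a univariable P value for each candidate. For gender, race, APACHE category and center, that P value measures association with death. For age, SOFA score and glucose, the only test named compares the randomised arms. No other part of the document tests these three factors against death; the mixed-model t-tests for SOFA and glucose also compare arms.

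A baseline difference between randomised arms arises by chance, so its P value says nothing about prognosis. If the text is followed, chance imbalance decides whether age, SOFA or glucose enters the mortality model. Stepwise selection can later drop a factor that entered by chance, but it cannot restore a predictor that was never entered. If the text is not followed, these three factors have no stated entry rule, and the choice is left until the data are in hand.

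**Working it through.** **The wording.** The rank-sum test takes two samples. The trial has three arms (0.6, 1.0 and 1.3 × REE), and the sentence does not say which pair is meant or how pairs would be combined. Kruskal-Wallis is named one paragraph later for three-arm comparisons. Died versus survived is a two-group split that suits the rank-sum test. The text therefore points to vital status as the intended grouping, but does not say so.

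**Inputs from the document.**
- Size, from the Abstract: "A total of 60 patients will be studied (20 per energy dose group".
- Allocation, from the randomisation section: "Treatment assignments will be stratified according to clinical center and on the basis of illness severity", in permuted blocks.
- Entry threshold P ≤ 0.20; "All statistical tests will be 2-sided".

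The document gives no power or error rate for this screen, so there is no planned figure to reproduce.

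**Assumptions, not in the document.** 28-day mortality 10%, 20% or 30%; log-odds of death per SD of the factor 0, 0.3, 0.7 or 1.0; block size 3 or 6; four equal strata (2 centers × APACHE II high or low); correlation of the factor with APACHE II 0 to 0.7.

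**Screen by arm, as written.** Under randomisation, P(pass) is about 0.20 for one test whatever the factor's effect on death. With three independent factors, the chance that at least one passes is 1 − 0.8³ = 0.488. Simulated pass rates (8,000 trials per setting), block 6 / block 3:

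| Correlation with APACHE II | Three-group test | One rank-sum pair | Any of three pairs |
|---|---|---|---|
| 0 | 0.198 / 0.200 | 0.196 / 0.194 | 0.405 / 0.397 |
| 0.5 | 0.143 / 0.153 | 0.159 / 0.160 | 0.337 / 0.338 |
| 0.6 | 0.133 / 0.126 | 0.147 / 0.143 | 0.320 / 0.310 |
| 0.7 | 0.104 / 0.099 | 0.126 / 0.124 | 0.278 / 0.274 |

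Rates fall as the correlation rises because stratifying on APACHE II balances related factors more tightly than chance alone would. A separate simulation without stratification (4,000 trials per setting) varied the odds ratio for death from 1 to 3 per SD. The by-arm rates stayed at 19% to 22% for one test and 39% to 42% for any of three pairs.

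**Screen by vital status.** Rank-sum test, 20,000 trials per setting, using trials with at least 2 deaths:

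| Mortality | Log-odds 0 | 0.3 | 0.7 | 1.0 |
|---|---|---|---|---|
| 10% | 0.204 | 0.300 | 0.589 | 0.785 |
| 20% | 0.192 | 0.355 | 0.752 | 0.920 |
| 30% | 0.200 | 0.402 | 0.836 | 0.961 |

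The separate simulation agrees: at an odds ratio of 2 per SD (log-odds 0.69) it gave 58%, 76% and 84%.

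**Joint example.** Assume log-odds of 0.7 for age, 1.0 for SOFA and 0 for glucose, all independent of each other and of APACHE II. By arm, both true predictors should enter with probability about 0.2 × 0.2 = 0.04, and neither with probability about 0.8 × 0.8 = 0.64. Simulation (8,000 trials, block 6) gave the following at mortality 10% / 20% / 30%:

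| Screen | Both enter | Neither enters |
|---|---|---|
| By arm | 0.041 / 0.042 / 0.038 | 0.647 / 0.632 / 0.641 |
| By vital status | 0.419 / 0.601 / 0.700 | 0.113 / 0.030 / 0.011 |

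**The case against.** The best defence is that the harmful reading is unlikely to be carried out. The variables are called prognostic, the sentences on either side concern association with mortality, and a rank-sum test cannot be run once across three arms. An analyst would have to stop and resolve the wording. Alternatively, the sentence may be an ordinary balance check, with the odds-ratio sentence supplying the univariable step: an odds ratio for a continuous factor normally comes from a logistic model, which also gives a P value.

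Both readings are plausible, but both are inferences. The odds-ratio sentence names no outcome, model or test for these factors, whereas the sentence before it names both a test and a grouping. On either reading the text needs the same correction.

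Three further points stand as limits.
- The simulated rates rest on assumptions absent from the document. The joint example in particular treats SOFA as independent of APACHE II.
- With 60 × 0.10 = 6 to 60 × 0.30 = 18 expected deaths and seven candidate factors, the model will be fragile even with a correct screen, so admitting more true predictors does not guarantee a stable fit.
- This is a pilot. Mortality is a secondary endpoint, and no hypothesis or specific aim asks for a mortality prognostic model.

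**Conclusion.** The concern holds. As written, the entry rule for age, SOFA score and blood glucose is wrong; read charitably, it is undefined. The central result needs only randomisation: a between-arm P value at baseline cannot respond to how well a factor predicts death.

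The size depends on the assumptions listed. By arm, a factor unrelated to APACHE II passes about 20% of the time with one test, or about 40% if any of three pairs counts. For a factor correlated 0.5 to 0.7 with APACHE II, the rates are 10% to 15% (three-group test), 12% to 16% (one pair) or 27% to 34% (any pair). By vital status the pass rate is 59% to 84% at log-odds 0.7 and 78% to 96% at 1.0. For a weak predictor (0.3) it is only 30% to 40%, so the gain there is small.

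The consequence is limited to the secondary mortality model. The primary infection analysis, the unadjusted mortality comparison between arms and the four categorical factors, including APACHE stratum, are unaffected. The correction should be made, but it does not threaten the trial's main conclusions.

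**What to change.** In the Aim 1 mortality paragraph, change the grouping for age, SOFA score and blood glucose from treatment arm to 28-day vital status, keeping the rank-sum test. Alternatively, name univariable logistic regression on 28-day death for these three factors, which also supplies the promised odds ratios.

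If a between-arm baseline comparison is wanted, describe it in a separate sentence as descriptive, use a method suited to three groups, and state that it does not feed the P ≤ 0.20 entry rule.

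The cost is one phrase, plus one sentence if the between-arm description is kept. No extra data or patients are needed, and the list of candidate factors does not change.

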gut microbiota in all fecal samples will be identified using established next generation DNA sequencing of 16S rRNA libraries, performed by our collaborator [name] of the University of Chicago (6, 18, 66). Briefly, 50 mg of frozen fecal sample will be homogenized in extraction buffer and 0.1-mm-diameter zirconia/silica beads are added prior to lysing of microbial cells on a Mini-Beadbeater-8 cell disrupter. After overnight incubation at 55°C, extraction with phenol: chloroform: isoamyl alcohol, and precipitation with ethanol will be performed. Isolated DNA is dissolved in Tris-EDTA buffer and stored at -80°C. The 16S rRNA gene sequences are amplified from DNA samples using barcode-labeled primers for the V3–V4 region of the 16S rRNA encoding gene (*Escherichia coli* positions 338–806), as outlined^{65–67}. The Shannon diversity index and distinctive peak numbers (richness) of the OTUs in the microbiome libraries between baseline (day 0) and serial fecal samples (days 3, 7, and 14) will be compared as previously outlined^{65, 67, 68}. These representative sequences are aligned using PyNAST and taxonomy assigned to them using the RDP Classifier. The PyNAST-aligned sequences will also be used to build a phylogenetic tree with FastTree and unweighted UniFrac distances then computed between all samples for additional ecological analyses, including principal coordinates analysis (PCA)^{65–67}.

Adverse Event (AE) Reporting:

The subjects enrolled in this trial are initially critically ill subjects deemed to require both PN and prolonged ICU care. Such individuals are known to have a high morbidity and mortality rate. No AEs specifically due to the study nutrient formulations are expected. However, we will closely monitor the clinical course of all subjects daily and record conventional serious adverse events (SAEs) and unexpected and expected AEs, as well as note significant clinical or surgical events as narrative data. For the purposes of study reporting, an SAE is any of the events below:

1. Death
2. Re-hospitalization after study PN or tube feeding discontinuation
3. Documented pulmonary aspiration of study tube feeds during study tube feed administration
4. New cancer diagnosis
5. Congenital anomaly/disorder

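### Screening at P≤0.20 and stepwise selection for 28-day mortality in 60 patients would give inflated odds ratios and intervals that undercover, in the secondary prognostic model only

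*Combined protocol and SAP*

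**What the plan says.** The relevant text is the mortality paragraph of Statistical Analysis, For Aim 1. The outcome is binary: "Twenty-eight day mortality will be summarized as a proportion plus the 95% confidence interval". Dose groups are compared on mortality by a chi-square or Fisher test, which stands apart from the prognostic model.

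Four factors are to be tested against death: "categorical prognostic factors (gender, race, high or low Apache score, clinical center) with mortality". Three more are handled differently: "Baseline continuous prognostic factors (age, SOFA score, blood glucose) will be compared by treatment group using the Wilcoxon rank-sum test". Then: "Factors significant to at least a value of $P \leq 0.20$ in the univariable analyses will be used in multivariable logistic regression analyses". Then: "Forward and backward stepwise selection will be used if necessary to choose prognostic variables for a multivariable logistic regression model". Each factor left in the final model gets an odds ratio and a 95% interval, adjusted for the others that remain.

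For this model the plan states no entry or stay threshold, no limit on the number of terms, no shrinkage or validation, no allowance for selection in the intervals, and no exploratory label.

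The sample size is in the Abstract: "A total of 60 patients will be studied (20 per energy dose group"). No mortality rate or death count appears anywhere. The Adverse Event Reporting section says only "Such individuals are known to have a high morbidity and mortality rate". Under Randomization of study subjects, "Treatment assignments will be stratified according to clinical center and on the basis of illness severity", so center and APACHE II stratum are design factors. The mortality paragraph treats both as ordinary candidates that may be dropped.

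**The concern.** The procedure looks at the outcome up to three times (univariable screen, multivariable fit, stepwise steps) and then reports the survivors as if the model had been fixed in advance. With few deaths, a factor survives mainly when its estimate happens to be large. The reported odds ratios are therefore too far from 1, and the intervals cover the truth less often than stated. At stake is whether a reader can trust the list of predictors of death and their odds ratios. Two further weaknesses sit in the same paragraph. The factors used to stratify randomization can disappear from the model, and the univariable P value for age, SOFA score and glucose is not a test against mortality as written.

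**Working it through.** The plan gives no figure to reproduce here beyond 3 × 20 = 60. Mortality and the stay level are assumptions.

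**Deaths per candidate.** Seven candidates: four categorical (race counted as binary; more categories would add terms) and three continuous.
- 15% of 60 = 9 deaths; 9/7 = 1.3
- 20% of 60 = 12 deaths; 12/7 = 1.7
- 25% of 60 = 15 deaths; 15/7 = 2.1

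**Passing the screen by chance.** For seven independent noise factors, P(at least one has P≤0.20) = 1 − 0.80^7 = 79%. Simulation with the actual discrete tests gives 66% to 85%.

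**Why survivors have large odds ratios.** Take a binary factor split 30:30 and find the smallest odds ratio that can pass P≤0.20:
- 9 deaths, split 7 v 2: (7×28)/(23×2) = 4.26
- 12 deaths: split 8 v 4 passes by chi-square, (8×26)/(22×4) = 2.36; Fisher needs 9 v 3, (9×27)/(21×3) = 3.86
- 15 deaths: split 10 v 5 passes by chi-square, (10×25)/(20×5) = 2.50; Fisher needs 11 v 4, (11×26)/(19×4) = 3.76

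**Keeping noise in the final model.** Null simulation: 60 patients, deaths fixed at 9, 12 or 15, independent factors, all factors tested by survival status, P≤0.20 screen, backward likelihood-ratio elimination, 2,000 runs per setting. Forward selection was not run separately. The five-factor column removes APACHE II and SOFA, which may truly predict death.

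| Assumed stay level | Noise factor kept, seven noise factors | Noise factor kept, five noise factors |
|---|---|---|
| 0.05 | 31–42% | 20–34% |
| 0.10 | 53–61% | 40–49% |
| 0.20 | 63–83% | 49–75% |

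Other simulations of the seven-factor null gave lower values at 0.05: 23% to 28% across 9, 12 and 15 deaths, and 25% at about 12 deaths. The last also gave 48% at 0.10 and 78% at 0.20. Part of the gap comes from the elimination test: in samples this small, likelihood-ratio elimination keeps factors more often than Wald elimination. The plan names neither. Taken together: about 25% to 40% at 0.05, and about half to four fifths at 0.10 to 0.20.

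The median odds ratio of a retained binary noise factor is about 3 to 9. In the tabulated simulation a noise factor has a Wald 95% interval excluding 1 in 20% to 31% of trials with seven noise factors. At 6 deaths (10% mortality) the retained odds ratios are larger still, and at a stay level of 0.05 more than half of those for binary factors come from separated or nearly separated fits.

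**When the factors do have effects.** With modest true effects and about 12 deaths, retained log odds ratios were about two to three times the true values. Their nominal 95% intervals covered the truth in 71% to 87% of cases. A seven-factor Firth model with no selection covered about 97%. The exact figures move with the assumed effects and stay level: smaller true effects and a stricter stay level make inflation and undercoverage worse.

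**The case against.** The strongest reply is that selection is not what produces chance findings at 0.05. Seven independent tests give 1 − 0.95^7 = 30% with no selection at all. In null simulations, seven one-at-a-time odds ratios flagged at least one factor in 22%, 23% and 27% of trials at 9, 12 and 15 deaths, with median flagged odds ratios of 4.4, 4.2 and 3.8. All seven in one unselected ordinary model flagged one in 27%, 28% and 32%. This stands: few deaths and seven looks explain the false flags at that level, and no change of wording removes them. But it does not rescue the procedure. Showing only the survivors is what inflates the estimates and breaks coverage; a prespecified model shown in full does neither. At stay levels of 0.10 or 0.20, noise factors are also kept far more often.

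It is also fair that stepwise selection applies only if needed, that mortality is secondary, and that keeping APACHE II or SOFA could be correct.

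A reader might infer more than the documents support:
- *That the dose comparison is compromised.* It is a separate chi-square or Fisher test. The infection endpoint has its own Poisson and GEE analysis.
- *That dropping center or APACHE II stratum biases the dose effect.* The plan does not say that dose group enters this model. For the same reason the candidate count is seven, not nine with two dose terms.
- *That the later multicenter trial would be misdesigned.* The pilot is meant to inform it, but nothing says that these prognostic odds ratios will set its design.
- *That all seven factors are screened on death.* As written only four are. The other three are compared by treatment group, with a two-sample test although there are three groups, so their screening P value is undefined.

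**Conclusion.** The concern holds for the secondary prognostic model of 28-day mortality and goes no further. Retaining a pure noise factor is roughly a one-in-four to two-in-five event at a stay level of 0.05, and about even to four in five at 0.10 to 0.20. Those figures assume 9 to 15 deaths and that none of the seven factors matters; with five noise factors they fall but stay material. The firmer objection is to the estimates: about two- to threefold inflation on the log scale and 71% to 87% coverage, assuming about 12 deaths and modest real effects. The death count, stay level, elimination test and effect sizes are all assumed, because the plan fixes none of them. A cheap improvement, worth making before the data are analysed.

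**What to change.** Remove the P≤0.20 screen and the stepwise step. Fit one prespecified Firth logistic model for 28-day mortality that always includes APACHE II stratum and center, together with gender, race, age, SOFA score and glucose. Report every factor's odds ratio and 95% interval, significant or not, and label the model exploratory. State that univariable tests of age, SOFA and glucose compare patients who died with those who survived.

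This keeps the plan's own question, which factors go with death. If an adjusted dose effect on mortality is also wanted, that is a different question: fit a separate Firth model with dose group, APACHE II stratum and center. Its four terms would have 12/4 = 3 deaths each at an assumed 12 deaths, so it too will be imprecise.

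The cost is SAP wording only, with no extra patients, visits or data. The downside is wide intervals and no data-driven short list of predictors, which this number of deaths could not support anyway.
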